#### 5.2.5. Simulation for mCRM Design

*Extensive simulations were performed to compare the operating characteristics of various competing mCRM designs in order to fine-tune mCRM performance and choose the 'best' mCRM design. Below is a brief description of the simulation setup and key findings. All the simulations were performed in ADE (v3.0.2.1).*

*Different combinations of cohort sizes (2 or 3), maximum dose escalation allowed between cohorts (1, 2 or 3 doses), stopping rules (maximum number of 6, 9, 12, 15, 18 and 24 subjects on MTD), mCRM dose-toxicity model (power or hyperbolic-tangent), and starting dose (5 µg/kg or 8 µg/kg) were examined. Competing designs were evaluated under 6 different plausible scenarios of dose-TIE curves varying in steepness, location of the true MTD and overall toxicity level in the range of the dosing grid.*

*For each of the above competing designs, the operating characteristics were compared by scenario to evaluate the trade-off between precision of MTD estimation and study efficiency. The final chosen design is a mCRM design with cohort size of 3, a starting dose of 5 µg/kg, and the stopping rule with maximum 12 subjects on MTD using the hyperbolic-tangent dose-toxicity working model. Based on simulations, this design provides, on average, a more accurate estimate of MTD and comparable or less proportion of subjects receiving doses higher than the MTD than the conventional 3+3 design, with an acceptable increase in the average sample size. Details of the simulations were documented in a simulation report for this study.*

### 5.3. General Methods

All statistical analyses will be presented in descriptive summaries, graphical displays when appropriate, and data listings by dose group. Data will be reported in accordance with the Pfizer data standards.

Baseline characteristics, disposition, and selected exploratory efficacy data will be summarized based on the FAS by dose group.

TIEs will be summarized based on the TIE-evaluable set. All other safety data, exposure data, concomitant medications and non-drug treatments will be summarized based on the safety analysis set. PK/PD data will be summarized based on the PK/PD analysis set. Biomarker data will be summarized based on the biomarker analysis set. Immunogenicity data will be summarized based on the immunogenicity analysis set.

### **5.3.1. Analyses for Continuous Variables**

Descriptive statistics (number of non-missing values, number of missing values if applicable [ie, n(missing)] , mean, median, standard deviation [SD], minimum, and maximum) for continuous variables will be summarized for all subjects in the corresponding analysis set, by dose group, and by each planned measurement time point if applicable. Inter-quartile ranges (Q1, Q3) and 95% confidence intervals may be provided where meaningful. Geometric mean and coefficient of variation (cv) may be provided as necessary for certain PK parameters.

For all relevant endpoints, the change from baseline at a specific post-treatment visit will be calculated as the difference between the measurement at that visit and the baseline measurement. Fold change, defined as the ratio of the post-treatment to pre-treatment, may be used as needed. For graphical presentation, scatter plots of individual actual values and change from baseline will be generated by scheduled visits, and by dose group when applicable.

### **5.3.2. Analyses for Categorical Variables**

Summary statistics including the frequency counts and percentages will be summarized for all subjects in the corresponding analysis set and by dose group for all categorical variables. If there are missing observations, the frequency count and percentage of missingness may be presented as a separate category. For analysis that refers to certain visits, percentages based on the number of subjects who are still present in the study at that visit may also be presented, where appropriate.

### **5.3.3. Definition of Time Variables**

#### **5.3.3.1. Study Day**

Study Day will be derived with sponsor current data standards. Start day of study treatment is the day of the study drug administration, which is Day 1.

The study day for assessments relative to the start of study treatment (eg, adverse event onset) will be calculated as:

$$\text{Study day} = \text{Date of the assessment/event} - \text{Date of start of study treatment} + 1.$$

The study day will be displayed in all relevant data listings.

#### **5.3.3.2. Time since ICH Onset to Study Drug Start**

The time in hours from ICH onset to the administration of study drug will be derived from the number of minutes elapsed between the date and time of ICH onset collected from the

“Primary Diagnosis” eCRF page and the start date and time of study drug administration collected from the “Dosing Record” eCRF page.

### **5.3.3.3. Duration of Study Treatment**

The duration of the study drug administration will be derived from the number of minutes elapsed between the start date and time of dose administration, and the stop date and time of dose administration collected from the “Dosing Record” eCRF page.

### **5.3.3.4. Duration of Hospital or Outpatient Rehabilitation Stay**

Health resource utilization is an exploratory endpoint. The hospital admission and discharge dates are collected for four categories of hospital unit: Intensive Care Unit (ICU), general ward (medical/surgical unit), in-patient rehabilitation center, and Other hospital units. The outpatient rehabilitation center admission and discharge dates are also collected. The duration of stay for each type of hospital unit or outpatient rehabilitation center will be derived as follows:

For non-missing discharge date:

$$\text{duration of stay (days)} = \text{date of discharge} - \text{date of admission}$$

For an ongoing stay, the date of last contact can be derived from the assessment dates described in Section 5.4.4.2:

$$\text{duration of stay (days)} = \text{date of last contact} - \text{date of admission}$$

The duration of main hospital stay (ICU/general ward) includes the duration of stay in ICU and general ward. It can be derived as follows:

$$\text{ICU/general ward admission date} = \min(\text{non-missing date of ICU admission, non-missing date of general ward admission})$$

$$\text{ICU/general ward discharge date} = \max(\text{non-missing date of ICU discharge, non-missing date of general ward discharge})$$

$$\text{Maximum length of ICU/general ward stay} = \text{ICU/general ward discharge date} - \text{ICU/general ward admission date}$$

$$\text{duration of main hospital stay} = \text{Maximum length of ICU/general ward stay} - \text{duration of stay in hospital units other than ICU and general ward during the ICU/general ward maximum stay period}$$

If a discharge date is missing and the stay is ongoing, the date of last contact will be used to calculate the corresponding duration. In the event of death during hospital or outpatient rehabilitation stay, the date of death will be used to calculate the duration of the corresponding health facility unit.

For each type of hospital unit or outpatient rehabilitation center, if a subject is admitted and discharged on the same date, the corresponding duration will be assigned as 0.5 day.

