2.2. Endpoints

Primary Endpoint:

- Frequency of treatment emergent thromboembolic and/or ischemic events (TIEs) in subjects treated with PF-05230907 through Day 8.
- Treatment emergent serious adverse events as characterized by type, frequency, severity, timing, seriousness and relationship to study treatment through Day 43.

- Treatment emergent adverse events as characterized by type, frequency, severity, timing, seriousness and relationship to study treatment through Day 8.
- Treatment emergent laboratory abnormalities as characterized by type, frequency, and severity through Day 4 (Day 8/discharge for D-dimer).
- Physical examination changes through Day 8 (or discharge).
- Vital sign changes through Day 8 (or discharge).
- ECG results through Day 8 (or discharge).

Secondary Endpoints:

- Changes in aPTT and PF1+2 after dosing with PF-05230907 through Day 2.
- ADA/neutralizing antibody (NAb) and Factor X activity through Day 43 and/or Day 91 follow-up visit.

Exploratory Endpoints:

- ICH absolute and percent change from baseline volume at 24 hours (see [SOA](#)).
- PF-05230907 concentration in plasma.
- Change in other exploratory biomarkers that may reflect pharmacologic effect of PF-05230907 or ICH progression may be evaluated.
- Potential biomarkers of neuro-inflammation and/or neurological outcomes to better understand ICH and/or its outcomes.
- CT parameters that may inform future investigations of PF-05230907 and/or the condition of ICH.
- Anti-Chinese hamster ovary (CHO) protein antibodies.
- Anti-paired basic amino acid cleaving enzyme (PACE) furin antibodies.
- Neurologic function as assessed by the NIHSS.
- Surrogate measures for health resource utilization, may include duration of stay in stroke/ICU unit, duration of hospital stay, duration of inpatient rehabilitation, and duration of outpatient rehabilitation.

Some of the planned biomarker(s) may not be performed if not supported by data from the ongoing pre-clinical work.

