6.3.1. Day 43 (±7 Days)

The following procedures will be completed:

- Collect the following blood samples:
 - Immunogenicity sample collections (ADA, NAb, FX activity, Anti-CHO and Anti-PACE) for shipment to a central laboratory.
- Conduct the mRS.
- Conduct the NIHSS.
- Document birth control utilized through the protocol required 28 days after the single dose of investigational product for male subjects who are able to father children and are sexually active and at risk of pregnancy, see [Section 4.4](#).
- Monitoring of serious adverse events.
- Monitoring of concomitant medications and treatments.
- Collect appropriate health resource utilization information which includes: as applicable, date subject began in-patient rehabilitation, discharge date subject completed in-patient rehabilitation, date subject began out-patient rehabilitation, and discharge date subject completed out-patient rehabilitation.

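### The SAP's main hospital stay formula counts days at home or in outpatient rehabilitation before a readmission as hospital stay, and the SAP does not say which unit category holds the stroke unit

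*SAP*

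**What the plan says.** SAP 5.3.3.4 says that dates are collected for four kinds of hospital unit: "Intensive Care Unit (ICU), general ward (medical/surgical unit), in-patient rehabilitation center, and Other hospital units". Outpatient rehabilitation dates are collected as well, but as a separate item and not as a hospital unit.

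The aim of the derived variable is stated plainly: "The duration of main hospital stay (ICU/general ward) includes the duration of stay in ICU and general ward". The derivation opens a window at the earliest non-missing ICU or ward admission and closes it at the latest non-missing ICU or ward discharge. From the length of that window it subtracts one thing, the "duration of stay in hospital units other than ICU and general ward during the ICU/general ward maximum stay period". No rule for readmission is given. A unit stay that begins and ends on one date is set to half a day.

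For open stays the SAP has a substitute end date: "For an ongoing stay, the date of last contact can be derived from the assessment dates". The later sentence on missing discharge dates also requires that the stay be ongoing.

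On the stroke unit, Protocol 2.2 lists "duration of stay in stroke/ICU unit" among the health resource measures, and SAP 3.3.6 repeats it. Schedule of Activities footnote n and Protocol 6.2.8 and 6.2.9 also collect stroke unit and ICU dates as one item.

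On timing, the Schedule of Activities continues health resource collection through Day 91, and footnote n includes ICU, stroke unit and hospital discharge dates. The Day 43 list in Protocol 6.3.1 covers rehabilitation only, including "discharge date subject completed in-patient rehabilitation, date subject began out-patient rehabilitation". The Day 91 list in 6.3.2 covers outpatient rehabilitation only.

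**The concern.** The deduction shows that the authors expected some stays to be interrupted, but it covers only one kind of interruption. Home is not a hospital unit, and the SAP itself treats outpatient rehabilitation as something other than one. Time in either place, falling between two recorded ICU or ward stays, therefore remains inside the window and is reported as hospital stay. That conflicts with the SAP's own description of the variable as ICU and ward time.

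The stroke unit is a second, conditional problem. Protocol 6.2.8 names it as one of the places where subjects may be confined through Day 4, yet SAP 5.3.3.4 and 6.3.6 refer only to ICU, general ward, in-patient rehabilitation and other units. Nothing in the documents says which category a stroke-unit stay takes. Placed under Other, it would be treated as time to remove.

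What is at stake is whether the listed duration means what its label says, both for readmitted subjects and, depending on coding, for stroke-unit subjects.

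**Working it through.** The documents state no figure here, so there is nothing to reproduce. The check applies the rule literally to illustrative histories, which are assumptions and not trial data. Numbers are study days of admission and discharge.

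SAP formula: latest ICU/ward discharge - earliest ICU/ward admission - days in in-patient rehabilitation or Other units inside that window.

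Comparator: sum of (discharge - admission) over the separate ICU and ward intervals.

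**Gaps before a readmission**

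| History | SAP formula | ICU + ward days |
|---|---|---|
| ICU 1-4, ward 4-8 | 8 - 1 - 0 = 7 | 3 + 4 = 7 |
| Same, then in-patient rehabilitation 8-30, ward 30-33 | 33 - 1 - 22 = 10 | 3 + 4 + 3 = 10 |
| Same, but home 8-30, ward 30-33 | 33 - 1 - 0 = 32 | 3 + 4 + 3 = 10 |
| Same, but outpatient rehabilitation 10-28 within the gap | 33 - 1 - 0 = 32 | 3 + 4 + 3 = 10 |
| Ward 1-10, home, ward 30-33 | 33 - 1 - 0 = 32 | 9 + 3 = 12 |

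The excess equals the length of the gap: 32 - 10 = 22 = 30 - 8 in the third and fourth rows, and 32 - 12 = 20 = 30 - 10 in the last. The first two rows show where the formula works.

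**Stroke unit, by coding**

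| History | Coded as Other | Coded as ICU |
|---|---|---|
| ICU 1-2, stroke unit 2-9, ward 9-12 | 12 - 1 - 7 = 4 | 1 + 7 + 3 = 11 |
| ICU 1-2, stroke unit 2-6, ward 6-9 | 9 - 1 - 4 = 4 | 1 + 4 + 3 = 8 |
| Stroke unit 1-5, ward 5-9 | 9 - 5 = 4 | 4 + 4 = 8 |
| Stroke unit 1-8 only | no ICU or ward date, undefined | 8 - 1 = 7 |

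In the first two rows the stroke-unit days are subtracted. In the third they fall before the window opens and are lost.

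**Late discharge dates.** Under Protocol 6.2.9, a subject still in hospital after Day 8 has the discharge-visit procedures on Day 8, before a discharge date exists. The Day 43 and Day 91 lists do not ask for that date later; footnote n does. A site working from the visit lists could leave it uncollected, while a site working from footnote n would not.

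**Same-date rule.** A plain sum of episodes would bring in a small error of its own. ICU 1-1 followed by ward 1-8 sums to 0.5 + 7 = 7.5 days, although the stay spans 8 - 1 = 7.

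**The case against.** The best defence is that the formula was meant for one index admission, for which it is right, and that a readmission may never reach the data because the Day 43 and Day 91 lists ask only for rehabilitation dates. This has some force. The home-gap error needs the later ICU or ward dates to be recorded, and if the visit lists governed collection they often would not be. The two collection concerns therefore cannot both be given full weight. But the SAP does not restrict the variable to the index admission, and the schedule continues collection to Day 91. Once a later stay is recorded, the rule returns the wrong value.

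On the stroke unit, every document passage that mentions its stay dates pairs it with ICU, so coding it as ICU is the natural reading. A reader might infer that stroke-unit days will be subtracted. The documents do not support that, because nothing places the stroke unit under Other. What stands is that the assignment is not written down.

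A reader might also infer that any discharge date missing after Day 8 is replaced by the date of last contact, which would greatly lengthen the stay. The SAP does not say so. The substitution requires the stay to be ongoing, and a discharged subject with a missing date does not meet that condition. The error would need a discharged subject to be recorded as still in hospital.

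Finally, SAP 6.3.6 only lists these durations, with unit-level durations beside them, so an odd value has some chance of being noticed.

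**Conclusion.** The point holds in a limited form. The main hospital stay formula is wrong for any subject with a recorded ICU or ward readmission after time at home or in outpatient rehabilitation, and the overstatement is exactly the length of the gap (20 days in the 32-against-12 illustration). It is right for continuous stays and for gaps in in-patient rehabilitation. This follows from the wording alone and assumes only that the readmission dates are in the data. How often that happens cannot be told from the documents.

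The stroke-unit point is an omission that could cause an error under one coding choice. The visit lists and footnote n disagree, so some later discharge dates may go uncollected.

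The consequence is small. The variable is exploratory, is presented without any planned summary or test, and covers a study stopped after 21 subjects were enrolled. This is a worthwhile tidy-up and not a threat to any conclusion of the trial.

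**What to change.** 1. In SAP 5.3.3.4, define main hospital stay as the days covered by the ICU and general ward intervals. Equivalently, keep the present window and also deduct any days within it that fall outside every hospital unit. Apply the half-day rule only when the whole main stay is a single date, so that a same-day transfer adds nothing.
2. State in SAP 5.3.3.4 that stroke-unit stays belong to the ICU category, as Protocol 2.2 and SAP 3.3.6 imply.
3. Align Protocol 6.3.1 and 6.3.2 with Schedule of Activities footnote n, so that ICU, stroke-unit and hospital discharge dates after Day 8 are collected at both visits, and in-patient rehabilitation dates at Day 91. The Day 43 list already has the in-patient rehabilitation dates.

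The cost is one revised formula and one sentence in the SAP, and a line in each of the two visit lists. Because the SAP amendment was written after the decision to stop the study, the third change may come too late for subjects who have finished follow-up; for them, missing dates would have to be queried.

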### **5.3.4. Standard Derivations and Reporting Conventions**

The following conversion factors will be used to convert days into weeks and months: 1 week = 7 days, 1 month = 30.4375 days

Demographics and physical measurements:

- Age (years):
  - $(\text{date of study treatment start} - \text{date of birth} + 1) / 365.25$ ;
  - In case of missing day, the missing day will be imputed as 15 for the calculation
  - In case only year of birth is given:  
 $\text{Age (years)} = (\text{year of study treatment start} - \text{year of birth})$ .

The integer part of the calculated age will be used for reporting purposes.

The following conversion factors will be used to convert pounds into kilogram (kg), inches and centimeters (cm) into meter (m): 1 pound = 0.4536 kg, 1 inch = 0.0254 m, 1 cm = 0.01 m.

- $\text{BMI (kg/m}^2\text{)} = \text{weight (kg)}/[\text{height (m)}]^2$

For reporting conventions, mean and median should generally be displayed one more decimal place than the raw data and standard deviation should be displayed to two more decimal places than the raw data. Percentages will be reported to one decimal place. Rounding can be performed to the closest integer or the targeted decimal place using the common mid-point between the two consecutive values. Eg, 6.1 to 6.4 can be rounded to an integer of 6, and 6.501 to 6.549 can be rounded to 6.5.

### **5.3.5. Unscheduled Visits**

Generally, data collected at unscheduled visits will be included and analyzed for all analyses in the same fashion as the data collected at scheduled visits except where otherwise noted. Unless otherwise noted, descriptive statistics by nominal visit such as laboratory measurements and vital signs will include only data from scheduled visits unless the scheduled visit measurement is missing, and needs to be replaced by an unscheduled visit that fall into the time window permitted for analysis purpose (see Section 5.4.5).

## **5.4. Methods to Manage Missing Data**

### **5.4.1. Missing Data**

All data will be evaluated as observed, and no imputation method for missing values will be used unless otherwise specified.

In all data listings, imputed values (if any) will be flagged. For missing statistics, for example, the measure of variability (SD) cannot be computed when N=1, ‘ND’ (Not Done) or ‘NA’ (Not Applicable) will be presented.

#### **5.4.2. Pharmacokinetic Concentrations and Parameters**

##### **5.4.2.1. PF-05230907 Concentrations Below the Limit of Quantification**

In all data presentations except listings, PF-05230907 concentrations assayed as below the limit of quantification (BLQ) will be set to zero. In listings BLQ values will be reported as “<LLQ”, where LLQ will be replaced with the value for the lower limit of quantification.

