Treatment emergent changes in clinical safety laboratory values were generally small and sporadic, with no clinically significant changes in hematology including platelet count, PT/INR, fibrinogen, ATIII, cardiac troponin I, or D-dimer (Day 7 and on). Dose dependent modulation of Protein C and Protein S activity, when analyzed with a clot based assay, were observed. Non-clinical studies indicate these changes reflect pharmacologic activity of the drug.⁶ Protein C activity and free Protein S level measured using non-clot-based assays for the 3 and 5 $\mu\text{g}/\text{kg}$ dose groups showed no treatment-related reduction. No subject had an adverse event (AE) related to abnormal laboratory test results and no subject met the pre-specified stopping rule criteria.

One weak and transient anti-drug antibody (ADA) response was detected in one subject from the 3 $\mu\text{g}/\text{kg}$ cohort at a single time point of Day 29. ADA results for the same subject on Day 1 (baseline), Day 15, Day 43, and the 6 month follow-up were negative. The positive anti-drug antibody did not cross react with native factor X or factor Xa and had no neutralizing activity. Based on all the available data, the sponsor, investigator, and the study eDMC determined that this finding did not alter the benefit risk profile of PF-05230907 for the intended indication of intracerebral hemorrhage.

Based on the PK data for all the subjects enrolled in the study, peak plasma concentration of PF-05230907 (C_{\max}) was reached between 2 to 5 minutes post-dose and PF-05230907 concentration declined very rapidly thereafter. In all subjects except one (from the 5 $\mu\text{g}/\text{kg}$ dose group), plasma PF-05230907 concentration was non-detectable by 40 minutes after dosing. The terminal half-life was calculated for 3 and 5 $\mu\text{g}/\text{kg}$, which are 4.6 (coefficient of variation [CV] =8%) and 3.7 (CV=2%) minutes respectively. Exposure appeared to increase dose-proportionally, especially at the higher doses where PK can be characterized more accurately. The very fast clearance of PF-05230907 is consistent with the observations in non-clinical studies.

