7.4. Pharmacokinetics

Blood samples will be collected at times specified in the [Schedule of Activities](#).

The actual times may change but the number of samples will remain the same. All efforts will be made to obtain the pharmacokinetic samples at the exact nominal time relative to dosing. However, samples obtained within 10% of the nominal time (eg, within 6 minutes of a 60 minute sample) from dosing or ± 2 minute for samples less than 10 minutes from dosing will not be captured as a protocol deviation, as long as the exact time of the sample collection is noted on the source document and data collection tool (eg, CRF).

Details regarding the collection, processing, storage and shipping of the blood samples will be provided to the investigator site in the study laboratory manual prior to initiation of the trial.

- Samples will be analyzed using a validated analytical method in compliance with Pfizer standard operating procedures.
- The PK samples must be processed and shipped as indicated to maintain sample integrity. Any deviations from the PK processing steps, including any actions taken, must be documented and reported to the sponsor. On a case-by-case basis, the sponsor may make a determination as to whether sample integrity has been compromised.
- As part of understanding the pharmacokinetics of the study drug, samples may be used for metabolite identification and/or evaluation of the bioanalytical method. This data will be used for internal exploratory purposes and will not be included in the clinical study report. Samples collected for this purpose will be retained in accordance to local regulations and if not used within this timeframe, will be destroyed.

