### **3.3.3. Pharmacokinetics**

*PF-05230907 concentration in plasma* is an exploratory endpoint. Blood samples will be collected at screening, 5 minutes and 45 minutes post-dose for this evaluation. *Samples obtained within 10% of the nominal time (eg, within 6 minutes of a 60 minute sample) from dosing or  $\pm 2$  minute for samples less than 10 minutes from dosing will not be captured as a protocol deviation.*

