##### **5.4.2.2. Deviations, Missing Concentrations and Anomalous Values**

In summary tables and plots of median profiles, concentrations will be set to missing if at least one of the following cases is true:

1. A concentration has been collected as ND (Not Done) or NS (no sample).
2. A deviation in sampling time is of sufficient concern or a concentration has been flagged anomalous by the pharmacokineticist.

Summary statistics will not be presented at a particular time point if more than 50% of the data are missing.

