### 6.3.3. Pharmacokinetics

PF-05230907 concentration in plasma is an exploratory endpoint. There will be  $C_{5\text{min}}$  and  $C_{45\text{min}}$  denoting the plasma concentration at 5 minutes and 45 minutes post-dose, respectively. *Available plasma concentration of PF-05230907 will be descriptively summarized and plotted by nominal PK sampling time and dose group. Due to the short half-life ( $t_{1/2}$ ) and limited sampling, noncompartmental parameters will not be calculated for the study report.*

Presentation of pharmacokinetic data will include:

- Descriptive statistics (n, mean, SD, %CV, median, minimum, maximum) of plasma concentrations will be presented in tabular form by dose group and nominal time.
- Dose-normalized  $C_{5\text{min}}$  and  $C_{45\text{min}}$  will be summarized using data pooled across dose groups in which different PF-05230907 doses were administered.

As data permit, pharmacokinetic data from this study may be analyzed using modeling approaches and may also be pooled with data from other studies to investigate any association between PF-05230907 exposure and biomarkers or significant safety/efficacy endpoints. The results of these analyses, if performed, may be reported separately.

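### Pooled dose-normalised C45min, with BLQ values set to zero, will be an uninformative zero or a low-biased mean driven by the assay limit and dose mix, unless the LLQ is low

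*SAP*

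**What the plan says.** SAP 3.3.3 sets the PK schedule: "Blood samples will be collected at screening, 5 minutes and 45 minutes post-dose for this evaluation". The 45-minute draw is therefore the only PK sample after the 5-minute one.

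SAP 5.4.2.1 gives the handling rule: "PF-05230907 concentrations assayed as below the limit of quantification (BLQ) will be set to zero". Listings are the exception and show the value as below the stated LLQ.

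SAP 6.3.3 plans two summaries. In the first, n, mean, SD, %CV, median, minimum and maximum of "plasma concentrations will be presented in tabular form by dose group and nominal time". In the second, dose-normalised C5min and C45min "will be summarized using data pooled across dose groups in which different PF-05230907 doses were administered".

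SAP 5.4.2.2 has one suppression rule: "Summary statistics will not be presented at a particular time point if more than 50% of the data are missing". In that section a value becomes missing if the sample was not done or not taken, if its timing deviation is of sufficient concern, or if it was flagged as anomalous. BLQ is not on the list.

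Protocol 1.3.2 reports the first-in-human results at doses up to 5 µg/kg. In all subjects except one, from the 5 µg/kg group, "plasma PF-05230907 concentration was non-detectable by 40 minutes after dosing". The terminal half-lives at 3 and 5 µg/kg are given as those "which are 4.6 (coefficient of variation [CV] =8%) and 3.7 (CV=2%) minutes respectively".

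**The concern.** Dose normalisation is meant to remove dose, so that subjects from different cohorts can be averaged. A BLQ value recorded as zero is still zero after division by any dose. Under dose-proportional PK, low doses fall below the LLQ more readily than high doses. Zeros then come mainly from the low-dose cohorts and positive values from the high-dose cohorts, so dose re-enters through the censoring.

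The pooled mean, SD and %CV of C45min/dose could then describe the assay limit and the dose mix rather than the drug. SAP 2.2.1 says that the number of subjects per dose cannot be fixed in advance, so the dose mix is itself a product of the adaptive allocation. Because zeros are not missing, the figure would be reported even if every 45-minute value were BLQ.

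At stake is an exploratory PK description that might later be set beside other studies, since SAP 6.3.3 foresees pooling PK data across studies.

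**Working it through.** **Inputs from the documents.** Cmax at 5 µg/kg is 46.13 ng/mL (Protocol 1.5), the peak falls at 2 to 5 minutes, and the half-life is 4.6 or 3.7 minutes (Protocol 1.3.2). Exposure is taken as linear in dose (Protocol Table 1, footnote a).

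**Assumptions.** Decline is mono-exponential from a peak at 5 minutes, and the healthy-volunteer half-life carries over to ICH patients. The LLQ is not in the documents, so it is varied from 0.05 to 1 ng/mL.

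**1. Reproduce the plan's figure.** 46.13/5 × 47 = 433.62 ng/mL, as in Table 1. The same scaling reproduces all 15 Cmax entries.

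**2. Half-lives elapsed.** 45/4.6 = 9.8 and 45/3.7 = 12.2. For the 5-minute sample, 5/4.6 = 1.1 and 5/3.7 = 1.4, so C5min is not affected.

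**3. Expected C45min.** C45 = (46.13/5) × dose × 2^(−40/t½). The factor 2^(−40/t½) is 0.00241 at 4.6 minutes (slow) and 0.000557 at 3.7 minutes (fast). C45 per µg/kg is therefore 0.0223 (slow) or 0.00514 (fast) ng/mL.

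| Dose (µg/kg) | Slow (ng/mL) | Fast (ng/mL) |
|---|---|---|
| 5 | 0.111 | 0.026 |
| 8 | 0.178 | 0.041 |
| 12 | 0.267 | 0.062 |
| 24 | 0.534 | 0.123 |
| 47 | 1.05 | 0.241 |

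With the peak at 2 minutes and fast decline, the 5 µg/kg value falls to about 0.015 ng/mL.

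**4. A check that does not need the LLQ.** Under linearity, C45 at dose D divided by C40 at 5 µg/kg equals (D/5) × 2^(−5/t½), which is 0.47 × D/5 (slow) or 0.39 × D/5 (fast). The ratio stays below 1 until D reaches about 11 (5/0.47) to 13 (5/0.39) µg/kg. If assay sensitivity is similar, 45-minute values at 5, 6, 8 and 10 µg/kg should mostly be BLQ, because C40 at 5 µg/kg was already undetectable in nearly everyone.

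**5. Dose at which C45 reaches the LLQ.** This is LLQ divided by 0.0223 (slow) or 0.00514 (fast).

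| LLQ (ng/mL) | Slow (µg/kg) | Fast (µg/kg) |
|---|---|---|
| 0.1 | 4.5 | 19.5 |
| 0.25 | 11.2 | 48.7 |
| 0.5 | 22.5 | 97.3 |

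With fast decline and an LLQ of 0.25 or more, the whole grid up to 47 µg/kg is zero. With slow decline and an LLQ of 0.1, every dose from 5 µg/kg upward is expected to be quantifiable.

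**6. Effect on the pooled mean.** Take two hypothetical mixes of 21 subjects. Mix A has 9 at 5, 6 at 8 and 6 at 12 µg/kg. Mix B has 3 each at 5, 8 and 12, and 6 each at 19 and 30. With slow decline, no between-subject spread and an LLQ between 0.178 and 0.267, the 5 and 8 µg/kg values become zero. The pooled mean is then 6/21 = 29% of true in A and 15/21 = 71% in B, although true C45/dose is identical.

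Simulating slow decline with a 10% between-subject spread in half-life gives a true mean of 0.0257 and these reported means:

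| LLQ (ng/mL) | Mix A | Mix B |
|---|---|---|
| 0.05 | 0.0253 | 0.0256 |
| 0.1 | 0.0227 | 0.0246 |
| 0.2 | 0.0146 (57%; 62% BLQ) | 0.0211 (82%; 29% BLQ) |
| 0.5 | 0.0029 (11%; 95% BLQ) | 0.0122 (47%; 67% BLQ) |

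**7. By-dose %CV.** For three values 0, 0 and c, the mean is c/3 and the SD is c/√3, so %CV = 100 × √3 = 173, whatever c is.

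**8. Sampling time.** SAP Table 4 accepts 15 to 75 minutes for this sample: 15/4.6 = 3.3 to 75/3.7 = 20.3 half-lives. A draw at 15 rather than 45 minutes raises the expected concentration by 2^(30/4.6) to 2^(30/3.7), about 90 to 280 times. One early draw among zeros could dominate a mean.

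**The case against.** The best defence is that little depends on this statistic and much of what is needed is already planned. PK is exploratory. The mCRM uses TIEs only, and SAP 7.4.2 says PK data are not required for moving to the next cohort. By-dose tables include the median and minimum, where zeros would show, and listings give BLQ results with the actual limit. The extended window applies only after review, and SAP 5.4.2.2 lets a badly timed sample be set to missing. All of this stands and keeps the point minor. It does not rescue the pooled statistic, which has no BLQ count attached.

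Four stronger readings are tempting, and the documents do not support them.

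- **A known size, or a false signal of more-than-proportional PK.** A reader might infer either from the slow-decline figures. They need slow decline and an intermediate LLQ. The 4.6-minute half-life was measured at 3 µg/kg; at 5 µg/kg it was 3.7 minutes, and at an LLQ of 0.25 or 0.5 that makes every grid dose zero, with no dose-mix effect.
- **The BLQ rule leaves only one usable time point.** That follows from the sampling schedule. The plan acknowledges limited sampling when it drops noncompartmental parameters.
- **SAP 5.4.3 shows an inconsistency.** It imputes half the detection limit for laboratory assays such as TFPI, not for the administered drug. Half the LLQ divided by dose would also depend on dose.
- **The draw should be moved.** Protocol 7.4 says "The actual times may change but the number of samples will remain the same", but SAP section 1 records the sponsor's decision to terminate early after 21 subjects were enrolled, so no enrolment remains for a new draw time.

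**Conclusion.** The concern holds for one statistic, pooled dose-normalised C45min. Many of its inputs, especially at the lower doses, are likely to be BLQ and so zero. Under exact dose proportionality three outcomes are possible:

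- a uniform zero, with fast decline or a high LLQ;
- a mean biased low by an amount set by the LLQ and dose mix, as with slow decline and an intermediate LLQ;
- a figure little affected, if the LLQ is low (about 0.1 ng/mL or less with slow decline).

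The documents do not say which applies, because they give no LLQ. The first-in-human result makes the third less likely under slow decline: C40 at 5 µg/kg would be about 0.24 ng/mL (46.13 × 2^(−35/4.6)), which an assay with an LLQ of 0.1 should have detected.

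The percentages above illustrate the mechanism and do not estimate the bias in this trial. They rest on mono-exponential decline, linear PK, healthy-volunteer half-lives and hypothetical dose mixes. The 15 to 75 minute window adds a further distortion that none of them includes. Severity is minor: neither the MTD nor any cohort decision rests on this figure.

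**What to change.** In SAP 6.3.3:

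- Delete the pooled dose-normalised C45min and keep the pooled summary for C5min.
- Report C45min by dose group as number and percent quantifiable, with the LLQ and actual sampling times.
- Give mean, SD and %CV of C45min only for dose groups in which at least half the values are quantifiable.

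The cost is SAP wording and a small change to table shells. No new data are needed: Protocol 7.4 already asks for the exact collection time to be recorded, and SAP 5.4.2.1 already requires the LLQ in listings. The sampling schedule stays as it is.
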